5.5. Justification for Dose

Refer to each investigation-specific addendum for information about the dose(s) selected for each study arm in that addendum.

6. Study Population

Prospective approval of protocol deviations to recruitment and enrollment criteria, also known as protocol waivers or exemptions, is not permitted.

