6.1. Inclusion Criteria

Patients are eligible to be included in the study only if they meet all of the following criteria of the CAMPFIRE Master Protocol and the additional criteria for enrollment provided in the protocol addendum to which they are enrolling. Any investigation-specific exceptions to the following criteria in a specific investigation will be described in that addendum; Sections 3.5.1.1 and 3.5.2.1.

- [1] have either measurable or evaluable disease using standard techniques by the Response Evaluation Criteria in Solid Tumors, Version 1.1 (RECIST 1.1) (Eisenhauer et al. 2009).
- [2] The patient, or patient's parent/guardian, has given written informed consent (and assent, as applicable) and authorization for release of health/information for research prior to any study-specific procedures being performed (refer to [Appendix 2](#), Study Governance, Regulatory, and Ethical Considerations).
- [3] The patient has a Lansky (<16 years of age; Lansky et al. 1987) or Karnofsky (\geq 16 years of age; Karnofsky et al. 1948) performance score of at least 50.
- [4] Patients must have discontinued all previous treatments for cancer or investigational agents \geq 7 days after the last dose or as shown below, and must have recovered from the acute effects to \leq Grade 2 for alopecia and decreased tendon reflex and to \leq Grade 1 for all other effects at the time of enrollment, unless otherwise noted. For agents with known AEs occurring beyond the required wait period outlined in the table, this period must be extended until after the time during which the AE is known to occur. Consult with the Lilly CRS/CRP for the appropriate length of time prior to the first dose of study treatment on additional therapies not mentioned.

Previous Treatment	Length of Time Prior to First Dose of Study Treatment
Cytotoxic and myelosuppressive chemotherapy	\geq 14 days after the last dose of cytotoxic or myelosuppressive chemotherapy (or \geq 42 days if prior nitrosourea)
Hematopoietic growth factors	\geq 14 days after the last dose of a long-acting growth factor (for example, pegfilgrastim) or \geq 48 hours for short-acting growth factor
Cellular therapy	\geq 42 days after the completion of any type of cellular therapy (eg modified T cells, NK cells, dendritic cells, etc.) agent
Interleukins, interferons, and cytokines (other than	\geq 21 days after the completion of interleukins,

Previous Treatment	Length of Time Prior to First Dose of Study Treatment

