hematopoietic growth factors)	interferon, or cytokines (other than hematopoietic growth factors)
Antibody therapy	≥21 days after the last infusion of antibody therapy
Radiotherapy	≥ 14 days since local palliative radiation therapy (RT) (small port); craniospinal XRT, or 50% or greater pelvic radiation; ≥ 42 days for other substantial radiation (such as metaiodobenzylguanidine therapy)
Radiopharmaceutical therapy (eg, radiolabeled antibody, 131I-MIBG)	≥42 days after systemically administered radiopharmaceutical therapy
Stem cell infusion without TBI	≥84 days must have elapsed after auto-transplant or stem cell infusion
Corticosteroids	≥14 days for patients who have received a course of systemic corticosteroids (≥5 days) to modify immune AEs related to prior therapy. Note: Patients who are on chronic replacement dose for endocrine disorders or are on a stable or decreasing dose for indications other than treating the underlying cancer, may still be eligible (consult Lilly CRP/CRS)
Live vaccines	≥28 days after last live vaccine

[5] The patient has adequate hematologic and organ function ≤1 week (7 days) prior to first dose of study drug:

System	Laboratory Value
Hematologic	
ANC	$\geq 1000/\mu\text{L}$ G-CSF permitted up to 48 hours prior. Patients with documented history of benign ethnic neutropenia or other conditions could be considered with a lower ANC after discussion with and approval from the Lilly CRP/CRS
Platelets	$\geq 75,000/\text{mm}^3$ Platelet transfusion permitted up to 72 hours prior.
Hemoglobin	$\geq 8 \text{ g/dL}$ ($\geq 80 \text{ g/L}$) Transfusions to increase the patient’s hemoglobin level to at least 8 g/dL are permitted; however, study treatment must not begin until 7 days after the transfusion. and CBC criteria for eligibility are confirmed within 24 hr of C1D1
Hepatic	
Total bilirubin	$\leq 1.5 \times \text{ULN}$ Except patients with document history of Gilbert Syndrome who must have a total bilirubin level of $< 3.0 \times \text{ULN}$
ALT and AST	$\leq 2.5 \times \text{ULN}$ OR $\leq 5.0 \times \text{ULN}$ if the liver has tumor involvement

Abbreviations: ALT = alanine aminotransferase; ANC = absolute neutrophil count; AST = aspartate aminotransferase; CBC = complete blood count; ULN = upper limit of normal.

- Creatinine clearance or radioscope glomerular filtration rate (GFR) $\geq 60 \text{ mL/min/m}^2$ (Appendix 4) OR
- Serum creatinine meeting the following parameters:

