 - for patients ≥ 18 years of age serum creatinine $\leq 1.5 \times$ upper limit of normal (ULN);
 - for patients < 18 years of age, serum creatinine based on age/gender as follows:

Age	Maximum Serum Creatinine (mg/dL)	
	Male	Female
1 to < 2 years	0.6	0.6
2 to < 6 years	0.8	0.8
6 to < 10 years	1.0	1.0
10 to < 13 years	1.2	1.2
13 to < 16 years	1.5	1.4
16 to < 18 years	1.7	1.4

The threshold creatinine values in this table were derived from the Schwartz formula for estimating glomerular filtration rate (Appendix 4).

- [6] Female patients of childbearing potential must have a negative urine or serum pregnancy test within 7 days prior to Cycle 1 Day 1.
- [7] Both female and male patients of childbearing potential must agree to use highly effective contraceptive precautions during the trial and for at least 3 months following the last dose of study drug, or longer, if appropriate for other study drugs according to their label in order to prevent pregnancy.

Females of childbearing potential (FOCBP) and males who are abstinent (if this is complete abstinence, as their preferred and usual lifestyle) or in a same-sex relationship (as part of their preferred and usual lifestyle) must agree to either remain abstinent or stay in a same-sex relationship without sexual relationships with someone of the opposite sex. Periodic abstinence (e.g., calendar, ovulation, symptothermal, or postovulation methods), declaration of abstinence just for the duration of a trial, and withdrawal are not acceptable methods of contraception.

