Appendix 4. Creatinine Clearance Formula

Note: This formula is to be used for calculating creatinine clearance (CrCl) from **local laboratory results only**.

Patients ≥ 18 years old

Cockcroft-Gault prediction of creatinine clearance from serum creatinine (1976)

For serum creatinine concentration in mg/dL:

$$\text{CrCl} = \frac{(140 - \text{age}^a) \times (\text{wt}) \times 0.85 \text{ (if female), or } \times 1.0 \text{ (if male)}}{72 \times \text{serum creatinine (mg/dL)}} \text{ (mL/min)}$$

For serum creatinine concentration in $\mu\text{mol/L}$:

$$\text{CrCl} = \frac{(140 - \text{age}^a) \times (\text{wt}) \times 0.85 \text{ (if female), or } \times 1.0 \text{ (if male)}}{0.81 \times \text{serum creatinine } (\mu\text{mol/L})} \text{ (mL/min)}$$

^a Age in years, weight (wt) in kilograms.

Source: Cockcroft and Gault 1976.

-OR-

Patients < 18 years old will use the Schwartz formula for the determination of creatinine clearance.

All Females and Pre-adolescent Males:

$$C_{\text{cr}} \text{ (mL/min/1.73 m}^2\text{)} = 0.55 \times \text{Height (cm)} / S_{\text{cr}} \text{ (mg/dL)}$$

Adolescent Males:

$$C_{\text{cr}} \text{ (mL/min/1.73 m}^2\text{)} = 0.70 \times \text{Height (cm)} / S_{\text{cr}} \text{ (mg/dL)}$$

Note: C_{cr} = creatinine clearance and S_{cr} = serum creatinine.

Source: Schwartz et al. 1976; Schwartz and Gauthier 1985.

Appendix 5. Protocol Amendment J1S-MC-JAAA(b) Summary CAMPFIRE: Children's and Young Adult Master Protocol for Innovative Pediatric Research

Overview

Protocol J1S-MC-JAAA CAMPFIRE: Children's and Young Adult Master Protocol for Innovative Pediatric Research has been amended. The new protocol is indicated by amendment (b) and will be used to conduct the study in place of any preceding version of the protocol.

The overall changes and rationale for the changes made to this protocol are as follows:

- An inclusion criterion was added to clarify that age requirements will be specified in the protocol addenda
- Additional detail was added to the Benefit/Risk Assessment
- A current estimate of investigations to be added to the master protocol construct was added to Section 7.8.1

Revised Protocol Sections

Note: Deletions have been identified by strikethroughs . Additions have been identified by the use of underscore .
--

Section 3.3 Benefit/Risk Assessment

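### The renal eligibility threshold is written per m², a unit neither Appendix 4 formula returns; read literally it is 103.8 mL/min/1.73 m², which does not fit the creatinine caps beside it

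*Protocol*

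**What the plan says.** Criterion [5] in Section 6.1 offers two alternative ways to show adequate renal function. The first is a clearance or GFR limb: "Creatinine clearance or radioscope glomerular filtration rate (GFR) $\geq 60 \text{ mL/min/m}^2$ (Appendix 4) OR". The second is a serum creatinine limit, which is 1.5 × ULN for patients of 18 and over and an age- and sex-specific table for those under 18. Of that table the protocol says: "The threshold creatinine values in this table were derived from the Schwartz formula for estimating glomerular filtration rate (Appendix 4".

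Appendix 4 gives the formulas to which the clearance limb refers. For patients under 18 it uses Schwartz, with constant 0.55 for girls and pre-adolescent boys and 0.70 for adolescent boys. Both lines print the result per 1.73 m²: "C_{\text{cr}} \text{ (mL/min/1.73 m}^2\text{)} = 0.55 \times \text{Height (cm)} / S_{\text{cr}} \text{ (mg/dL" and "C_{\text{cr}} \text{ (mL/min/1.73 m}^2\text{)} = 0.70 \times \text{Height (cm)} / S_{\text{cr}} \text{ (mg/dL". For patients of 18 and over it uses Cockcroft-Gault, whose denominator and unit read "72 \times \text{serum creatinine (mg/dL)}} \text{ (mL/min", with no indexing to body surface area.

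Two further statements govern how strictly the criterion binds. Section 6 says: "Prospective approval of protocol deviations to recruitment and enrollment criteria, also known as protocol waivers or exemptions, is not permitted". Section 6.1 leaves one way out: "Any investigation-specific exceptions to the following criteria in a specific investigation will be described in that addendum".

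**The concern.** The threshold and the formulas that are meant to feed it are in different units. A site with a Schwartz result or an indexed measured GFR can compare its number directly with 60, or convert and require 103.8. A site with an adult Cockcroft-Gault result can compare it directly with 60, or divide it by body surface area first. Each reading can be defended from the page, and they give different decisions for the same patient.

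What is at stake is who gets in. The clearance limb exists to admit patients whose creatinine is above the cap but whose filtration is adequate. If the literal unit makes that limb almost impossible to meet, children with relapsed cancer are turned away for a misprint. A site that sensibly corrects the unit enrols patients who fail the written criterion, which leads to the inadvertent-enrolment procedure of Section 8.1.1. Section 3.3 relies on common eligibility criteria to keep investigations consistent, and Section 7.8.1 expects about ten investigations under this master protocol. Each inherits the criterion unless its addendum says otherwise.

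**Working it through.** **Inputs.** The threshold (60 mL/min/m²) and the creatinine caps are from Section 6.1, criterion [5]. The formulas, constants and units are from Appendix 4. Heights, body surface areas and adult ULNs are not in the protocol and are marked as assumptions.

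**Step 1: convert the threshold.** 60 mL/min per 1 m² × 1.73 = 103.8 mL/min/1.73 m², and 103.8 / 60 = 1.73, so 73% higher. Conversely, 60 mL/min/1.73 m² would be written 60 / 1.73 = 34.7 in the printed unit.

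**Step 2: test against the creatinine caps.** If the caps come from Schwartz, then height = target × cap / k. The height in cm that each cap implies is:

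| Age and sex | Cap (mg/dL) | k | Target 60 | Target 70 | Target 103.8 |
|---|---|---|---|---|---|
| 1 to <2 | 0.6 | 0.55 | 65.5 | 76.4 | 113.2 |
| 2 to <6 | 0.8 | 0.55 | 87.3 | 101.8 | 151.0 |
| 6 to <10 | 1.0 | 0.55 | 109.1 | 127.3 | 188.7 |
| 10 to <13, girls and pre-adolescent boys | 1.2 | 0.55 | 130.9 | 152.7 | 226.5 |
| 10 to <13, adolescent boys | 1.2 | 0.70 | 102.9 | 120.0 | 177.9 |
| 13 to <16, boys | 1.5 | 0.70 | 128.6 | 150.0 | 222.4 |
| 13 to <18, girls | 1.4 | 0.55 | 152.7 | 178.2 | 264.2 |
| 16 to <18, boys | 1.7 | 0.70 | 145.7 | 170.0 | 252.1 |

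At 103.8 every height but one is out of reach for its age band. The exception, an adolescent boy of 10 to <13 at 178 cm, is merely very tall. At 60 to 70 the heights are broadly those of children, though not every cell fits equally well.

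The same check can be run forwards. Assume heights of 72–90 cm (1 to <2), 82–120 (2 to <6), 108–145 (6 to <10), 128–165 (10 to <13), 145–185 for boys and 145–175 for girls (13 to <16), and 160–190 for boys and 150–178 for girls (16 to <18), and treat boys of 13 and over as adolescent. The caps then give Schwartz values of about 56 to 86 mL/min/1.73 m², and up to 96 for an adolescent boy of 10 to <13. None reaches 103.8.

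**Step 3: what the literal unit does to the clearance limb.** A child above the cap can reach 103.8 by Schwartz only if taller than the last column of the table. On that route the alternative is therefore nearly empty.

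**Step 4: who is caught.** These are children above the cap who still have a Schwartz value of at least 60 per 1.73 m². The upper end of the creatinine window is k × height / 60. At assumed heights:

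- 110 cm, 2 to <6: 0.55 × 110 / 60 = 1.01, so >0.8 to 1.01 mg/dL
- 135 cm, 6 to <10: 0.55 × 135 / 60 = 1.24, so >1.0 to 1.24
- 160 cm girl, 13 to <18: 0.55 × 160 / 60 = 1.47, so >1.4 to 1.47
- 175 cm adolescent boy, 16 to <18: 0.70 × 175 / 60 = 2.04, so >1.7 to 2.04

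**Step 5: adults.** The literal cut-off is 60 × body surface area. At assumed areas of 1.5, 1.73 and 2.0 m² it is 90, 103.8 and 120 mL/min, which is 50%, 73% and 100% above an unindexed 60. The creatinine alternative limits the effect. Assume age 20 and a ULN of 1.2 mg/dL for men and 1.0 for women, so caps of 1.8 and 1.5. A 70 kg man reaches 60 mL/min up to 120 × 70 / (72 × 60) = 1.94 mg/dL, a window of 0.14. A 60 kg man reaches it only up to 120 × 60 / (72 × 60) = 1.67, and a 60 kg woman up to 0.85 × 1.67 = 1.42. Both are below the cap, so neither has a window.

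**The case against.** The strongest reply is that this is a unit slip with a limited practical effect. The criterion refers to Appendix 4, the Schwartz lines there print 1.73 m², and most sites would compare the result with 60 without converting. The loss of a patient needs several things together: creatinine above the cap, clearance between 60 and 103.8, a site that applies the written unit, and no exception in the addendum. No endpoint, sample size or error rate depends on it. The windows vanish for shorter children (at or below 87.3 cm at 2 to <6, 109.1 cm at 6 to <10, and 152.7 cm for girls of 13 to <18) and for many adults. The 60 to 70 target is inferred, and limbs joined as alternatives need not be equivalent. The addenda, which could restate the unit, are not at hand, and Section 8.1.1 covers patients later found ineligible.

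Most of this stands as a limit on size. It does not make the threshold right. That sites may quietly correct it is itself the difficulty, because a correction made at one site and not at another gives different enrolment decisions under one criterion. The argument from the caps does not need the limbs to be equivalent: it shows that 103.8 cannot be the value behind them, and that at 103.8 the Schwartz limb admits almost nobody whom the cap does not already admit. The ANC row allows the sponsor's physician to approve a lower value, but the renal limb has no such route.

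**Conclusion.** The threshold is wrong as written and should be corrected. The unit mismatch and the conversion to 103.8 mL/min/1.73 m² follow from the protocol alone. That the intended value is about 60 per 1.73 m² is an inference from the creatinine caps, since the protocol does not state the target.

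Under the literal reading, patients above the cap with an indexed clearance or measured GFR of 60 to <103.8 are excluded. The creatinine windows shown rest on assumed heights and run from 0.07 mg/dL wide (the 160 cm girl) to 0.34 mg/dL (the 175 cm boy, 2.04 − 1.7). The protocol gives no basis for counting the patients in them, or those decided on measured GFR. The literal error admits nobody with worse renal function, so the harm is wrongful exclusion and inconsistent enrolment, not a safety risk.

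**What to change.** In criterion [5], change the clearance limb to ≥60 mL/min/1.73 m² for patients under 18 and for any measured GFR reported per 1.73 m².

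For patients of 18 and over, choose one rule and state it: either unindexed Cockcroft-Gault of at least 60 mL/min, or Cockcroft-Gault normalised to 1.73 m² before comparison with 60. The two are not the same. At an assumed body surface area of 2.0 m², an unindexed 60 mL/min is 60 × 1.73 / 2.0 = 51.9 mL/min/1.73 m², so the choice is a clinical one and should be made explicitly.

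Confirm the target from which the creatinine caps were derived, and check whether any open addendum repeats the unit. The cost is a one-line protocol amendment, with no extra data and no extra patients.

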6.2. Exclusion Criteria

Patients will be excluded from the study if they meet any of the following criteria. Additional exclusion criteria for each study arm are provided in the applicable study arm-specific protocol addendum. Exceptions, where applicable, to the following criteria will be defined in each specific addendum.

- [8] Patients with severe and/or uncontrolled concurrent medical disease or psychiatric illness/social situation that in the opinion of the investigator could cause unacceptable safety risks or compromise compliance with the protocol.
- [9] Patients who have active infections requiring therapy.
- Patients with an active fungal, bacterial, and/or known severe viral infection including, but not limited to, human immunodeficiency virus (HIV) or viral (A, B, or C) hepatitis (screening is not required).
- [10] Patients who have had allogeneic bone marrow or solid organ transplant are excluded.
- [11] Surgery: Patients who have had, or are planning to have, the following invasive procedures are not eligible:
- Major surgical procedure, laparoscopic procedure, or significant traumatic injury within 28 days prior to enrollment.
 - Central line placement or subcutaneous port placement is not considered major surgery.
 - Core biopsy, fine needle aspirate, and bone marrow biopsy/aspirate are not considered major surgeries. Refer to the specific addenda to determine if results are required prior to enrollment.
 - Surgical or other wounds must be adequately healed prior to enrollment.
- [12] Female patients who are pregnant or breastfeeding are excluded.
- [13] Patients who are currently enrolled in a clinical study involving an investigational product, or any other type of medical research judged not to be scientifically or medically compatible with this study.

6.3. Lifestyle Restrictions

This section is not applicable unless otherwise stated in the specific protocol addendum.

6.4. Screen Failures

Individuals who do not meet the criteria for participation in the individual investigation (screen failure) may be re-screened only after discussion with and with permission from the Lilly CRP/CRS or designee. Individuals who do not meet criteria for participation in an individual investigation may be considered for another investigation within the CAMPFIRE Master Protocol.

Screening laboratory tests may not be repeated more than twice in order to meet eligibility during the screening period.

Repeating laboratory tests during the screening period, after a patient has not met requisite criteria, does not constitute re-screening.

7. Treatments

7.1. Treatments Administered

Administration of the study drug(s) is described in the applicable protocol addendum.

A delay of a dose due to holiday, weekend, bad weather, or other unforeseen circumstances will be permitted as specified in each addendum and not counted as a protocol deviation. However, clinical assessment time frames relative to drug administration, as shown in the addendum schedule of activities, must be maintained.

Patients may continue to receive study treatment until a criterion for discontinuation is met. See Section 7.8.1 for information about continued access to study treatment after the primary analysis for a given study arm.

The investigator or his/her designee is responsible for the following:

- explaining the correct use of the drug(s) and planned duration of each individual's treatment to the patient/study site personnel/legal representative
- verifying that instructions are followed properly
- maintaining accurate records of study treatment dispensing and collection
- at the end of the study returning all unused medication to Lilly, or its designee, unless Lilly and sites have agreed all unused medication is to be destroyed by the site, as allowed by local law.

7.1.1. Packaging and Labelling

Typically, study drugs will be provided by Lilly, but commercially available supply may be site-sourced where local regulations permit or for cases of regional restrictions or supply limitations.

Clinical study materials will be labeled according to the country's regulatory requirements.

7.2. Method of Treatment Assignment

The CAMPFIRE Master Protocol and its addenda may consist of both single and multi-arm investigations. Assignment to treatment arms in an investigation will be determined by a computer-generated random sequence using an interactive web response system (IWRS). Randomization ratios will be described within addenda when they contain multiple arms. When patients are eligible for more than one investigation (ie, more than one investigation is ongoing for a given patient population) they will be randomly assigned across investigations to one of the open treatment arms. If there is a common treatment arm among addenda, the randomization ratios between that common arm and other treatments within each addenda will determine the overall ratios across addenda. For example, Addendum 1 has a randomization ratio of 2:1 experimental regimen A to control and Addendum 2 has a randomization ratio of 3:1 experimental regimen B to control; the overall randomization is 2:3:1 for experimental regimen A to experimental regimen B to control. When arms are not shared across addenda, each new

addendum will specify the relative weighting between its arms and those of the previously opened addenda.

Some addenda may incorporate adaptive treatment randomization methodology, in which case the adaptation rules will be described in the addendum. Allocation to treatment across addenda will follow the rules described above for fixed randomization designs.

Participating in one investigation does not preclude the patient from enrolling in another investigation within the CAMPFIRE Master Protocol at a subsequent time as long as eligibility criteria are met. Individuals who do not meet criteria for participation in an individual investigation may be considered for another addendum within the CAMPFIRE Master Protocol for which they are eligible (see Section 6.4).

